#### 10.1.4 Analysis of safety parameters

Safety parameters should be evaluated at each visit planned in this study, as well as at unscheduled visits.

Safety evaluation will be based on the following parameters (between Visits 1 and 3), compared between the investigational medicinal product and placebo:

Frequency of adverse events (AEs) and/or serious adverse events (SAEs) in the treatment groups, including:

1. Determination of the overall incidence in:
  - I. adverse events (AEs), regardless of their association to the treatment;
  - II. AEs related or possibly related to the medicinal product administration;
  - III. AEs requiring therapy discontinuation.

AEs recording will be based on spontaneous report by the patient, as well as on the results of a patient survey by a physician.

Adverse events will be encoded according to the last update of MedDRA terminology. They will be represented by a preferred term (PT) and a system organ class (SOC).

2. AEs incidence according to the results of the vital signs evaluation (HR, BP, BT, RR) at each visit vs placebo

Changes in the main vital signs over time and the frequency of pathological abnormalities revealed during physical examination will be summarized in groups, and a comparison will be made between groups using appropriate tests for quantitative and qualitative data (see below). Quantitative data will be compared using the t-test or the Mann-Whitney test, depending on the normality of the distribution (which will be evaluated using the Shapiro-Wilk test). Qualitative data will be compared using the Fisher's exact test or the chi-square test, depending on the number of prospective observations in one cell (<5 or ≥5).

3. AEs incidence according to the results of laboratory examinations on Days 7(± 2) and 15(± 2) and AEs incidence according to the ECG results 15(± 2) vs placebo;

Variations in the results of laboratory tests (carried out in the central laboratory) over time and the rate of pathological deviations from the norm of the study results (based on the central laboratory reference values), as well as the deviations rate of the ECG results at the Visit 3 will be summarized by groups, and comparison between groups shall be made using appropriate tests for quantitative and qualitative data (see paragraph 2).

4. AEs incidence according to the everyday patients' diaries records of well-being self-evaluation.

Patient complaints based on the results of the daily records of well-being self-assessment in the diary will be summarized into groups, and comparison between groups shall be made using appropriate tests for quantitative and qualitative data. Gastrointestinal AEs (determined using standardized MedDRA requests for the corresponding symptoms), regarded by the Investigator as associated with the study therapy, will be analyzed separately. Descriptive statistics methods will be used for the results. Comparison of the incidence of new AEs in the study groups will be carried out using the Fisher's exact test or the chi-square criterion, depending on the number of prospective observations in one cell ( $<5$  or  $\geq 5$ ); the comparison of severity degree (and possible causal relationship between received medicinal product and AE) will be carried out using the Cochran – Armitage test for linear trends for ordered categorical data.

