#### 5.2.3.2.4. *Electrocardiography*

Electrocardiography (ECG) will be performed at visit 1 and at visit 3. The ECG includes the registration of an electrocardiogram in 12 leads (in 3 standard and 3 augmented limb leads, as well as, in 6 precordial leads) at rest in the supine position. ECG interpretation will be performed by a cardiologist, therapist or functional diagnostics practitioner.

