#### **5.2.4.4 Unscheduled Visits**

The unscheduled visits will be conducted when necessary, e.g., in case of the index disease deterioration, AEs development, or intolerability to therapy of LRG-002 medicinal product or placebo.

Every unscheduled visit, irrespective of its cause, must include the procedures listed below with completion of the relevant eCRF pages (Unscheduled Visit):

- Physical examination;
- Measurement of vital signs (BP, HR, RR, body temperature);
- A 12-lead ECG;
- AE assessment;
- Evaluation of the concomitant treatment;
- If indicated, any of the study procedures may be additionally performed upon the decision of the Principal Investigator.

Taking into account frequency of visits, unscheduled visits may be conducted on the same days as the scheduled ones but at a different time (e.g., in case of worsening the patient may visit the trial site in the afternoon).

Procedures for planned clinical study visits are the same in each treatment group during each study period.

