#### ***6.3.1.1 Timing and volume of data collection for excluded subjects.***

If the subject is excluded from the study at his/her request, the investigator should try to find out the reason for the termination of the study. If the study is terminated due to the occurrence of AE/SAE, monitoring of the subject continues until AE/SAE resolution. In case of premature termination of the patient's participation in the study, the patient is invited to the study site to carry out the procedures of premature study termination visit (carried out within the frameworks of unscheduled visit); if the patient refuses to visit the study site, the premature study termination visit is carried out by phone, while as much as possible the available information is recorded.

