8.1. Adverse events

Safety assessment will also be based on the following parameters (between Visits 1 and 3) compared between the investigational medicinal product and placebo:

Incidence of adverse events (AEs) and/or serious adverse events (SAEs) in the treatment groups including:

- Overall AE rate as compared to placebo;
- AE rate according to the results of physical examinations during each visit compared with placebo;
- AE incidence according to the assessment of the vital signs (HR, BP, BT, RR) at each visit as compared to placebo;
- AE incidence according to the ECG results on Day 15 (± 2) in comparison with placebo;
- AE incidence according to the results of laboratory examinations on Days 7 (± 2) and 15 (± 2) as compared to placebo;
- AE incidence according to the results of daily self-examination of the state of health recorded in Self-Observation Diary.

The study doctor will review the entries in the Self-Observation Diary. If the study doctor believes that the information in the Diary complies with the AE criteria, they will ask the patient about this event and document all information about the AE (including the causality assessment).

The AEs will be described according to the scheme given below:

- AE description
- Severity of the adverse event (meeting the severity criteria)
- AE severity
- AE duration
- Relation to the IMP
- Measures taken in relation to the investigational medicinal product
- Measures taken in relation to the patient

- **Outcome**

Adverse events will be coded according to the MedDRA

Methods of descriptive statistics will be used to represent the results. A comparison of the incidence of new AE cases in the study groups will be performed using the Fisher's exact test or the chi-square test, depending on the number of proposed observations in one cell (< 5 or ≥ 5), and a comparison of the severity (and the possible causality between the administered medicinal product and AE) will be conducted using the Cochran–Armitage test for linear trends for ordered categorical data.

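### The between-arm ECG deviation rate is taken at Visit 3 alone, with no within-patient comparison with Visit 1 and no stated place for unscheduled or early-termination ECGs

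*Protocol*

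**What the plan says.** **Collection.** Protocol 5.2.3.2.4 sets the scheduled recordings: "Electrocardiography (ECG) will be performed at visit 1 and at visit 3". Protocol 5.2.4.4 adds that "Every unscheduled visit, irrespective of its cause, must include the procedures listed below", and a 12-lead ECG is on that list. Protocol 6.3.1.1 describes the "premature study termination visit (carried out within the frameworks of unscheduled visit" procedures, so a patient who leaves early and attends the site should have an ECG. The same section allows that visit to be held by phone, in which case there is none.

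**Analysis.** Protocol 10.1.4 item 3 plans two ECG outputs:
- an adverse-event line, "AEs incidence according to the ECG results 15(± 2) vs placebo";
- a between-arm deviation rate: "as well as the deviations rate of the ECG results at the Visit 3 will be summarized by groups".

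SAP 8.1 repeats only the adverse-event line, "AE incidence according to the ECG results on Day 15 (± 2) in comparison with placebo". It gives no ECG deviation rate, no shift from baseline and no rule for unscheduled ECGs, and SAP 8.2 foresees no other safety endpoints.

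**Contrast within 10.1.4.** Item 3 also plans "Variations in the results of laboratory tests (carried out in the central laboratory) over time", and item 2 plans change over time for vital signs. The ECG is given a single cross-sectional rate.

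**The concern.** A rate of abnormal ECGs at one visit cannot show whether the abnormality arose on treatment. Findings present before the first dose count the same as new ones. With 1:1 randomisation they should be about equally common in the two arms, so they add noise and shrink the relative contrast.

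The rate also needs a Visit 3 recording. Patients who stop early have none, and Protocol 6.3.1 lists disease progression, intolerance of the product and clinically significant adverse events among the reasons for stopping. Their absence may therefore be informative, in either direction.

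Safety is the trial's stated secondary objective and the results are meant to support authorisation. An ECG table that cannot separate new from old findings is of limited use for that, although most of the recordings needed for a better one are already required.

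**Working it through.** **Step 1: the plan's own figure.** No figure is stated for the ECG comparison. The sample size is needed only to count patients who may lack a Visit 3 ECG. With 0.26 and 0.15, two-sided 0.05 and 80% power:

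(1.960 + 0.842)² / (0.26 − 0.15)² × [0.15 × 0.85 + 0.26 × 0.74] = 207.5, so 208 per arm; 208 / 0.80 = 260 per arm, 520 in total. Both figures reproduce.

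**Step 2: patients outside the Visit 3 rate.** At 20% withdrawal, 260 × 0.20 = 52 per arm, or 104 of 520. At 10% it is 26 per arm and at 5% it is 13. These are upper limits, since some patients counted as withdrawals or lost to the per-protocol set may still attend Visit 3.

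**Step 3: dilution (illustration only).** The ECG rates are assumptions. Let q be the share with an abnormality at Visit 1 that persists, and let i be the risk of a new abnormality among the rest.

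- Visit 3 rate = q + (1 − q) × i, with 208 per arm.
- New-abnormality rate = i among patients with a normal Visit 1 ECG: 260 × (1 − q) per arm if every withdrawn patient has a termination ECG, 208 × (1 − q) if none does.

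Example with q = 20%, i = 2% vs 8%: Visit 3 rates are 0.20 + 0.80 × 0.02 = 21.6% and 0.20 + 0.80 × 0.08 = 26.4%. A fourfold ratio becomes 26.4 / 21.6 = 1.22.

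Power by exact binomial enumeration of the Pearson chi-square test at two-sided 0.05:

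| New abnormality | q | Visit 3 rates | Visit 3-only power | New-only, all termination ECGs | New-only, no termination ECGs |
|---|---|---|---|---|---|
| 2% vs 8% | 5% | 6.9% vs 12.6% | 50% | 89% (n = 247) | 81% (n = 198) |
| 2% vs 8% | 20% | 21.6% vs 26.4% | 21% | 83% (n = 208) | 74% (n = 166) |
| 2% vs 8% | 30% | 31.4% vs 35.6% | 15% | 78% (n = 182) | 68% (n = 146) |
| 2% vs 4% | 5% | 6.9% vs 8.8% | 11% | 26% (n = 247) | 21% (n = 198) |
| 2% vs 4% | 20% | 21.6% vs 23.2% | 7% | 22% (n = 208) | 17% (n = 166) |
| 2% vs 4% | 30% | 31.4% vs 32.8% | 6% | 19% (n = 182) | 15% (n = 146) |

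Most of the gain comes from using Visit 1, because it survives when no termination ECG is available. Two simplifications apply. Worsening of an existing abnormality is not modelled. And the plan moves to Fisher's exact test when cell counts fall below 5, which is likely for new abnormalities (208 × 0.02 = 4.2 expected in the lower arm) and would lower those powers somewhat.

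**The case against.** The strongest reply is that the plan protects ECG safety elsewhere, and much of it stands.

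- A reader might infer that old abnormalities are counted as adverse events. They are not. Protocol 9.3.4 makes a condition that predates dosing an AE only if it is exacerbated, and limits which abnormal test results are AEs at all. The group comparisons in 10.1.4 and SAP 8.1 are of new AEs. The mixing of old and new applies only to the raw deviation rate.
- A reader might infer that the Visit 1 ECG is ignored. Protocol 10.1.1 and SAP section 5 compare pre-dose instrumental data between arms, with an additional adjusted analysis if the arms differ significantly. That is a group-level check and does not separate new from old findings within a patient, but the recording is used.
- A reader might infer that withdrawn patients are lost to the safety analysis. They stay in the safety population (Protocol 10.8, SAP 4.2.1), both documents say safety is evaluated at unscheduled visits, and an AE found on an unscheduled ECG enters the overall AE rate. These patients are missing only from the Visit 3 rate.
- The power gain depends on assumed rates. For 2% vs 4% neither analysis has useful power, and a low prevalence of baseline abnormality, which non-inclusion criterion 23 may favour, reduces the dilution. Nor is it established that most Visit 3 findings would be pre-existing: with q = 5% and 8% new, the share is 0.05 / 0.126 = 40%.

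What remains is narrower. The one planned ECG rate has no baseline reference within patients and no rule for post-dose ECGs other than Visit 3. The general sentence about unscheduled visits does not supply one, because item 3 names Visit 3 specifically.

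**Conclusion.** The point holds for the between-arm ECG deviation rate in Protocol 10.1.4 item 3, and only for that rate. It combines pre-existing with new abnormalities, which mainly pulls the comparison toward no difference, and it leaves out up to 52 patients per arm if the planned 20% withdraw before Visit 3. The effect of that omission could go either way.

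The loss of power is large if the true excess is large (2% vs 8%: 50% to 15%, against 89% to 78% with all termination ECGs or 81% to 68% with none). It is small in absolute terms if the excess is modest (2% vs 4%: 11% to 6%, against 26% to 19% with all termination ECGs). All of these rest on assumed ECG rates and on baseline abnormalities persisting to Visit 3. The trial is not sized for ECG findings. Severity is minor: a cheap improvement to a safety summary.

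**What to change.** In Protocol 10.1.4 item 3 and the SAP safety section, add:

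- the proportion of safety-set patients with an ECG abnormality new or worse than at Visit 1 on any post-dose ECG (Visit 3, unscheduled, or early termination where one was recorded);
- the denominator, stated as patients with at least one post-dose ECG, with the number lacking one shown by arm;
- a shift table from Visit 1 to the worst post-dose ECG, by arm;
- a risk difference with 95% CI.

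Keep the Visit 3 rate as a supportive table and carry it into the SAP, which does not currently contain it.

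The cost is wording and one extra table; no procedure, visit or patient is added. There are two limits: unscheduled ECGs are not at fixed times, so patients seen more often have more chances to show an abnormality, which is why the Visit 3 table should stay; and termination visits held by phone yield no ECG, so some patients will still be missing.

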## 10.2 Interim analysis

Interim data analysis is not planned in this study

## 10.3 Sample size calculation

Sample size calculation is based on the following actions:

1. Efficacy of probiotics in prevention of acute diarrhea: a meta-analysis of masked, randomized, placebo-controlled trials. Sazawal S, Hiremath G, Dhingra U, Malik P, Deb S, Black RE. Lancet Infect Dis. 2006 Jun; 6(6):374-82. Review. PMID:16728323. DOI:10.1016/S1473-3099(06)70495-9
3. McFarland LV. Meta-analysis of probiotics for the prevention of antibiotic associated diarrhea and the treatment of Clostridium difficile disease. Am J Gastroenterol. 2006 Apr;101(4):812-22.

5. H. Szajewska, M. Kołodziej. Systematic review with meta-analysis: Lactobacillus rhamnosus GG in the prevention of antibiotic-associated diarrhoea in children and adults. AP&T, Volume 42, Issue 10, November 2015, Pages 1149-1157.

Primary endpoint is the AAD incidence from 1 to the last day of LRG-002 administration vs placebo in ARD patients treated with standard antibiotic therapy. The primary efficacy criterion will be considered achieved if the odds ratio for the AAD incidence between two groups is significantly higher than 1 (i.e. AAD incidence in the LRG-002 group is lower than in placebo group).

A test based on odd ratio was used for sample size calculation.

The following data were obtained from Figure 2 in the meta-analysis [1] (only data on AAD were used):

- Given only data for AAD studies in adults from the cited publication, the rate for the control group is 0.24, and for the treatment group - 0.14.
- Given only data for LGG studies in adults and children, the rate for the control group is 0.26, and for the treatment group - 0.15.

In meta-analysis [14], figures from Table 1 demonstrate a rate of 0.196 for the treatment group and 0.29 for the placebo group (only trials for adults with LGG were taken into consideration).

In meta-analysis [15], figures from Table 2 demonstrate a rate of 0.188 for the treatment group and 0.269 for the placebo group (only trials for adults with LGG were taken into consideration).

Consideration of AAD studies for LGG from the paper[16], concerning infections in adults (including H.pylori), resulted in 0.14 for the probiotic group and 0.22 for the control group.

Combining all the strains, we obtained a rate of 0.26 for placebo and 0.15 for probiotic group.

The following indicators were used for calculations:

1. Difference of AAD absolute risks in placebo and treatment groups is expected to be positive.
2. Incidence of AAD is assumed 0.26 for a placebo group and 0.15 for the treatment group.
3. Likelihood of type I errors: 0.05;
4. Power of the study is 80%, which corresponds to the type II error: 0.20
5. Statistical hypothesis is the evidence of superior efficacy:

$H_0: OR=1$

$H_1 : OR \neq 1,$

wherein OR is the odds ratio between both groups.

The ratio between the treatment and placebo group sizes is 1:1

The number of patients in each group could be calculated using the following formula [2]:

$$n_T = n_R = \left( \frac{Z_{1-\alpha/2} + Z_\beta}{p_T - p_R} \right)^2 [p_T(1-p_T) + p_R(1-p_R)] = 208$$

Thus, we obtain the minimum number of patients required for statistical analysis - 416 (208 patients in each group). Given the 20% attrition rate, there is a necessity to randomize 520 subjects (260 patients in each group).

#### **10.4 Applicable significance level of the clinical study**

All statistical tests in this study will be conducted at a 95% significance level (the threshold p value for confirming statistical significance is less than 0.05). Bilateral statistical criteria will be applied for all parameters studied.

#### **10.5 Clinical study termination criteria**

The study may be terminated subject to occurrence of terms and conditions set forth in section 5.8 of this protocol.

#### **10.6 Missing, Suspect and Non-Amendable-To-Analysis Data Procedures**

During monitoring visits to the clinical center, Clinical Research Associates (Monitors) authorized by the Sponsor will analyze the CRF of the study subjects for the lack of necessary data. If there is any missing data in CRF and the relevant information is available in the source documentation, relevant queries to investigators shall be spelled out, as well as instructions for elimination of discrepancies. During check of the database, the Statistician, authorized by the Sponsor, and Managers for Data Control and Processing will determine whether there were any uncertain, missed, or non-amendable-to-analysis data, based on which queries to investigators can be defined. The investigators, if possible, eliminate the detected errors in CRF, and inform the Principal Investigator and authorized representatives of the Sponsor thereof. If the detected errors in the data cannot be eliminated after the completion of the patient's participation in the study, sensitivity of the resulting parameters to the presence of suspected data will be analyzed during the statistical analysis of the data. Information on missing, suspected and non-amendable-to-analysis data will be presented in the final clinical study report. For the primary endpoint, the method of filling in the missing values will be applied on the basis of the maximum likelihood estimation (MLE), if necessary [64]. For all other types of endpoints and other parameters, the analysis will be carried

out only using actually available information, without data fulfillment, which is associated with a short duration of the clinical study.

### **10.7 Procedures for reporting any deviations from the original statistical plan**

All deviations from the original statistical plan should be described and justified in an amendment to the protocol and / or the final study report (in the latter case, the statistical analysis plan developed prior to the initiation of the final statistical analysis should contain a list of these deviations with justification of reasons for deviating from statistical plan according to the Protocol).

### **10.8 Selection of subjects for analysis**

For the analysis, the following data sets will be used:

- Population of all included patients (intention-to-treat, ITT): all randomized subjects who administered at least one dose of the investigational medicinal product / placebo and completed at least one visit to evaluate the efficacy parameters (i.e. at least all procedures of visit 1).
- Population of patients who completed the study according to the Protocol (per protocol, PP): all randomized subjects who completed participation in the study according to the Protocol (completed the prescribed period of treatment and follow-up without significant deviations from the Protocol).
- Safety population: all randomized subjects who administered at least one dose of the investigational medicinal product / reference medicinal product and completed at least one visit to evaluate safety parameters (i.e. at least Visit 1). Unlike the ITT population, the safety population will be analyzed according to the actual treatment received rather than the prescribed treatment (if the differences are identified between the treatment prescribed and actually received).

## **11. Description of activities concerning Quality Control and Quality Assurance**

### **11.1 Study Monitoring and Quality Control**

Regular visits of the Clinical Research Associate (Monitor), on behalf of the Sponsor and in accordance with standard operating procedures (SOPs), prior to, during and in the end of the study, contribute to the study success, guarantee the collection of accurate data and the timely detection of possible errors, documenting the clinical trial process and ensuring the protection of the study

subject rights and the study relevance to the principles of Good Clinical Practice (ICH GCP) and requirements of international law and applicable legislation of the Russian Federation.

Routine study monitoring includes:

- Confirmation of the proper conduction and documentation of the informed consent process, as well as screening and inclusion of subjects in the study;
- Verification of CRF data and primary medical documentation of the study subjects;
- Confirmation of documentation and timely reporting of information on AEs during the study;
- Confirmation of compliance with the requirements for the implementation of diagnostic and therapeutic procedures of the study protocol by the personnel of the clinical center;
- Confirmation of documentation on delivery, storage, distribution and destruction of the investigational medicinal product / reference medicinal product and study materials;
- Confirmation of the personnel competencies of the clinical center, external laboratory, necessary for the study;
- Confirmation of the conformity of diagnostic and laboratory equipment to the requirements of safe and adequate use during the study;
- Confirmation of the Investigator's interactions with the local Ethics Committee on the study safety issues and the introduction of amendments to the study Protocol, approved by the Sponsor.

Quality control of the study results is carried out by the Sponsor / Sponsor's Qualified Person, maintaining an electronic study database, which determine inconsistencies, wrong data, missing data during the cross-validation of all CRFs. Should any questions or a need of clarification arise, a special form (request for data clarification) is sent to the Investigator in the eCRF system or by e-mail / fax, the request must be answered in written form within 7 days after its delivery.

In accordance with legislative requirements, the Sponsor or authorized government authorities have the right to verify (audit) the material and technical support of the study and its documentation. The Investigator shall provide access to documentation and all necessary information to persons authorized to conduct an audit or inspection.

Monitor visits can be carried out both face-to-face and remotely by agreement with the Sponsor. A detailed description and format of the visits will be provided in the Study Monitoring Plan.

